## **2.17 Rationale for the current trial**

The rationale for combining the high dose bolus aldesleukin with hydroxychloroquine includes potential positive interactions on the immune regulatory side, non-overlapping toxicities, and potential for prolongation and increased number of responses based on murine studies conducted at the University of Pittsburgh. This study is a multi-center phase II study designed to estimate the efficacy of combination therapy of standard high dose bolus IL-2 and various doses of hydroxychloroquine therapy in metastatic RCC patients. The combination of high dose bolus IL-2 and hydroxychloroquine has not been used in prior clinical trials. Hydroxychloroquine has been shown to be safe in other acute stressful situations such as operative procedures (127-130). Combinations of IL-2 with chloroquine have recently been shown in Pittsburgh to be statistically more effective than IL-2 alone, tested in three murine models (131). Based on this murine data, we could expect to double the complete response rate in patients. Use of the number of doses of IL-2 as a composite of maximum tolerated dose and dose limiting toxicity helps us (132, 133) deal with assessing the tolerability of the addition of a second drug to IL-2 designed to enhance efficacy

or decrease toxicity. Evaluating toxicity after 8 doses allows us to compare comparable amount of drug across patients when all are expected to have received all eight of the doses.

The primary outcomes for this study will be overall survival, progression-free survival and response rate. A secondary analysis will compare outcomes between the trial patients and a historical control set matched according to the prognostic criteria described by Motzer *et al* (20) [lactate dehydrogenase (> 1.5 upper limit of normal), hemoglobin (< lower limit of normal), corrected calcium (>10mg/dL), Karnofsky performance status (< 80%) and time from initial RCC diagnosis to start of interferon- $\alpha$  therapy of less than one year were significant prognostic factors. Patient categories are no risk factors, 1 or 2 risk factors, or 3 or more] (20).

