### 1.1 Primary:

1. Estimate the proportion of patients with metastatic RCC treated with IL-2 combined with hydroxychloroquine at 600 mg/d who experience a clinical complete response.

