## 13.0 STATISTICAL ANALYSIS AND STUDY SIZE

### 13.1 Objectives and Design

The primary objective of this Phase II trial is to estimate the proportions of patients with metastatic RCC treated with high-dose IL-2 combined with hydroxychloroquine experiencing complete response, or any response. The secondary objectives are to compare response, time to progression and survival to historical data to determine the toxicity of the treatment regimen, to evaluate PD, and to examine correlative science endpoints. Disease endpoints are defined in Section 10.

The accrual goal is 39 participants. All study participants will receive the same high-dose IL-2 treatment, which is considered standard of care. The initial dose of HCQ will be 600 mg/day for all patients. If no limitations on additional dosing (treatment-limiting toxicities [TLTs], as defined in Section 9.2), dosing will continue at 600mg/d, otherwise, HCQ will de-escalate to 400 mg/d. Toxicity and response will be monitored after every three patients (Section 13.4), and will be stopped if the probability that treatment with IL-2+HCQ is excessively toxic or ineffective. The study may be opened more broadly to additional Cytokine Working Group sites whenever sufficient evidence has accrued that treatment with IL-2+HCQ is no more toxic or less effective than treatment with IL-2 alone.

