### 13.2 Analysis Plan

The data will be analyzed for response, overall survival and other endpoints, as described in this section; data will only be analyzed as specified in Section 14.3.1 to ensure the toxicity of IL-2+HCQ is not unexpectedly high. All analyses will be performed using the most recent versions of SAS and/or R available.

- 13.2.1.** *Estimate the proportion of patients with metastatic RCC treated with IL-2 combined with hydroxychloroquine at 600mg/d who experience a clinical complete response.* Response is defined in Section 10.3. The probability of each category of response will be estimated. Secondary analyses will employ cumulative logit regression for increasing levels of response, with adjustment for demographic and clinical covariates. All point estimates will be accompanied by appropriate 95% confidence intervals.
- 13.2.2.** *Compare the response, overall survival and time to progression of patients with metastatic RCC treated with IL-2 combined with hydroxychloroquine to the published response of patients treated with high dose IL-2 alone.* Logistic and proportional hazards (Cox) regression will be used to compare clinical response, and OS and PFS, respectively, to examine the effect of HCQ on the efficacy of IL-2. Formal tests of non-inferiority are beyond the scope of this Phase II study, and these secondary analyses are not statistically powered.
- 13.2.3.** *Characterize the toxicity of IL-2 combined with hydroxychloroquine in patients with metastatic RCC: number of doses of IL-2 administered during the first course of therapy; toxicity after the scheduled 9th dose of IL-2; frequency of grade III and IV or unexpected or rare toxicities.* Number of doses, maximal toxicity grade and incidence of treatment-limiting toxicities (TLTs, as defined in Section 10.5) will be tabulated.

**13.2.4** *Evaluate the utility of known prognostic criteria for RCC patients on clinical outcome.* Prognosis is evaluated by whether the patient has 0, 1, or 2, or 3 or more of the following risk factors:

- lactate dehydrogenase (> 1.5 upper limit of normal)
- hemoglobin (< lower limit of normal)
- corrected calcium (>10mg/dL)
- Karnofsky performance status (< 80%)
- time from initial RCC diagnosis to start of interferon- $\alpha$  therapy of less than one year

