### 13.4 Justification of Design

The primary objective of this study is to estimate the clinical response rate of patients with metastatic RCC treated with IL-2 combined with hydroxychloroquine at 600mg/d. Assuming no TLTs occur and the trial is not closed early for toxicity or inadequate response (Section 13.3.2), there will be 39 patients available for this objective. A 95% exact binomial confidence interval on 5 responses out of 39 patients (expected if the addition of HCQ to IL-2 doubles the historic proportions of CR ~ 8%) would have width equal to 0.27 (0.07,0.34). For the secondary endpoints of OS and PFS, if patients are recruited over 15 months, observed for 15 additional months, and the true median survival is 16 months, then the expected width of the 95% confidence interval for median survival is 12.8 months.

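### The primary endpoint is stated inconsistently (complete response, any response, or OS/PFS/response rate), and the futility rule mixes the same response definitions

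*Combined protocol and SAP*

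**What the plan says.** The current text describes the primary endpoint in five places.

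- **Section 1.1**, under the heading for primary objectives, has a single item: "Estimate the proportion of patients with metastatic RCC treated with IL-2 combined with hydroxychloroquine at 600 mg/d who experience a clinical complete response".
- **Section 13.2.1** repeats it: "600mg/d who experience a clinical complete response".
- **Section 13.1** widens it to patients "experiencing complete response, or any response".
- **Section 13.4** says "The primary objective of this study is to estimate the clinical response rate of patients with metastatic RCC", then derives its expected count from doubling a historical CR proportion of about 8%.
- **Section 2.17** says "The primary outcomes for this study will be overall survival, progression-free survival and response rate".

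On survival, 13.4 uses the words "For the secondary endpoints of OS and PFS". Section 1.2 also places OS and PFS among the secondary objectives, and 13.1 does the same for survival and time to progression. No passage says which statement governs.

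The futility rule in 13.3.2 switches definition from one element to the next. Its opening sentence and its posterior criterion (rate below 0.10 with probability above 0.8) refer to partial plus complete responses. Its counting instruction and its prior (8 of 95) refer to complete responses. The Table 8 caption is titled for complete response but tells the reader to count partial or complete responses.

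**The concern.** This is a single-arm trial whose primary aim is estimation. Naming the headline quantity and its benchmark in advance is therefore the main protection against choosing them after the data are seen. As written, a report could cite the protocol in support of CR, any response, PFS or OS as primary.

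The choice changes the conclusion. High-dose IL-2 alone has a much lower CR rate than overall response rate, so one observed percentage can look like a doubling against one benchmark and like no gain against the other.

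The monitoring committee faces the same problem in real time. With the same patients and the same Table 8, it could halt or continue depending on which sentence of 13.3.2 it follows.

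**Working it through.** **1. The plan's own figures in 13.4.**
- The exact 95% interval for 5/39 (12.8%) is (0.043, 0.274), width 0.231. The plan prints (0.07, 0.34), width 0.27, which does not reproduce. Doubling 8% gives 0.16 × 39 = 6.2 expected CRs, not 5. Both are separate errors. What matters here is that the count is built from CR.
- The 12.8-month width for median survival does reproduce. With exponential survival, median 16 months, 15 months of uniform accrual and 15 more of follow-up, P(death) = 0.616. Expected deaths are 39 × 0.616 = 24.0, and the width is 2 × 1.96 × 16/√24.0 = 12.8.

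**2. Benchmarks, each ratio within one dataset.**

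| High-dose IL-2 source | CR | Overall response | Ratio |
|---|---|---|---|
| 255-patient series (2.2) | 17/255 = 6.7% | 37/255 = 14.5% | 37/17 = 2.2 |
| Phase III high-dose arm (2.3) | 8/95 = 8.4% | 22/95 = 23.2% | 22/8 = 2.75 |

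An observed 16% is 16/8.4 = 1.9 times the phase III CR rate. Read as overall response, it is close to the 14.5% of the series and below the 23.2% of the phase III arm.

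**3. Precision by endpoint (exact 95% intervals, n = 39).** CR near 16%: 6/39 gives (0.059, 0.305). Any response near 23%: 9/39 gives (0.111, 0.393). A statement built on one does not describe the other.

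**4. Which definition Table 8 was computed from.** For x responses in n patients and a Beta(a, b) prior, stop if P(p < 0.10) > 0.8 under Beta(a + x, b + n − x).

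- *CR prior, Beta(8, 87), from 8/95.* The largest stopping counts at n = 18, 21, 24, 27, 30, 33, 36 are 0, 1, 1, 1, 2, 2, 2, which is exactly Table 8. The posterior probabilities at those counts are 0.882, 0.823, 0.845, 0.865, 0.805, 0.827 and 0.848.
- *Overall-response prior from the same arm, Beta(22, 73), from 22/95.* No count stops the trial at any look. Even 0 of 36 gives a posterior probability of only about 0.01.

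So the printed boundary follows from CR data, although the criterion and the table instruction name partial plus complete response.

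**5. How the printed rule behaves.** I used an exact binomial recursion over the Table 8 looks, carrying forward only paths above the boundary. The first look can be checked by hand: P(0 of 18) = 0.92^18 = 0.223 at a true 8%, 0.84^18 = 0.043 at 16% and 0.77^18 = 0.009 at 23%.

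| True rate of the counted response | Stopped by n = 24 | Stopped by n = 36 |
|---|---|---|
| 8% (historical CR) | 50% | 62% |
| 16% (doubled CR) | 13% | 17% |
| 23% (historical overall response, phase III arm) | 3% | 4% |

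The n = 24 column is shown because 2.18 gives 5 + 21 = 26 patients at 600 mg/d. If only those count, later looks are not reached. The last row depends on the benchmark: at 15%, the overall response rate of the 255-patient series, the same recursion gives 21% by n = 36.

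**The case against.** The strongest reply is that the intent is clear. Section 1.1 lists one primary objective, 13.2.1 repeats it, the expected count in 13.4 comes from doubling CR, and the prior behind Table 8 is a CR count. Section 2.17 is background, still speaks of various hydroxychloroquine doses, and itself expects a doubling of CR. Section 13.4's wording is loose rather than a different endpoint. Reporting CR and any response as two nested proportions is also legitimate, and 13.2.1 estimates every response category anyway.

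Most of this stands, and it shows which way to reconcile. It does not remove the conflict. Sections 13.1 and 13.4 belong to the statistical section itself. Section 2.17 goes on to label the historical comparison a secondary analysis, so its ranking of OS and PFS as primary is not just loose phrasing. Reporting every category does not settle which result is the headline.

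Four stronger readings are tempting, but the documents do not support them.

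- *The trial has no primary question.* Section 1.1, taken alone, states one.
- *Several primary endpoints inflate the error rate.* No alpha, power or null hypothesis is given for the primary objective. CR is a subset of any response, and death counts in both PFS and OS, so an independence calculation does not fit. Relabelling endpoints as secondary would leave the same intervals in the report.
- *The precision calculation covers CR only.* Section 13.4 also gives an interval width for median survival.
- *The benchmarks differ fourfold.* That needs the Select trial's 28% overall response divided by the 7% CR of the 255-patient series, which are different trials. Section 2.2 gives no CR rate for Select.

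**Conclusion.** The point holds as an internal inconsistency. The primary endpoint is described in ways that cannot all be true, and the futility rule carries the same CR versus partial-plus-complete conflict. The evident intent is CR at 600 mg/d.

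The choice of definition moves the historical benchmark by about 2.2 to 2.8 times. It also moves the probability of stopping by 36 patients from 62% (true 8%) or 17% (true 16%) to 4% (true 23%). These probabilities assume that the printed counts are applied at every listed look, that responses are independent with a constant rate, and that the historical rates quoted in the plan are plausible. With the lower overall-response benchmark of 15% the last figure is 21%, so the contrast is smaller but still large against the 62% for historical CR.

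**What to change.** Make CR at 600 mg/d the sole primary endpoint, as 1.1 and 13.2.1 already state, and align the other sections:

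- **2.17:** list OS, PFS and overall response as secondary outcomes.
- **13.1:** move any response from the primary sentence to the secondary objectives.
- **13.4:** write complete response rate in the sentence that states the primary objective.
- **13.3.2:** reconcile the opening sentence, prior, criterion, counting instruction and Table 8 caption so that all use one response definition. If that definition is not the one the prior uses, recompute Table 8. A matching prior from the same arm with the current criterion gives no boundary at all, so the criterion would then need review too.

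The cost is wording in four sections, plus a short recalculation only if the futility rule is not to be based on CR. No new data or patients are needed. To be of value, the change must be made before the outcome data are analysed.

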### **2.18 Early experience with the regimen.**

The first five patients were treated with 600mg of Hydroxychloroquine with one patient deemed a complete response. Out of the 13 patients treated with combination HCQ/IL-2 therapy using 1200 mg of Hydroxychloroquine, two patients experienced pronounced hypotension and tachycardia. Furthermore, one patient died from pulmonary emboli, not attributed to therapy. The cardiac events are consistent with IL-2 toxicities, but were observed somewhat earlier in the course of treatment. For that reason we are accruing another 21 patients to assess response in addition to the first five patients at the lower 600mg/d dose.

## 3.0 ELIGIBILITY

### 3.1 Inclusion Criteria

- 3.1.i. Histologically confirmed metastatic renal cell carcinoma with predominantly clear cell histology.
- 3.1.ii. Have measurable disease by RECIST 1.1 criteria. For example, this would include tumor in the lung, liver, and retroperitoneum. Bone disease is difficult to follow and quantify and as a sole site would not be acceptable.
- 3.1.iii. Patients must be at least 4 weeks from radiation or surgery and recovered from all ill effects.
- 3.1.iv. Age  $\geq 18$  years.
- 3.1.v. Karnofsky Performance Status  $\geq 80\%$ .
- 3.1.vi. Adequate end organ function:
  - a. Hematologic: ANC  $\geq 1000$  cells/ $\mu\text{L}$ , platelets  $\geq 100,000/\mu\text{L}$ , hemoglobin  $\geq 9\text{g/dl}$  (pre transfusion values used for prognostic factor, can be transfused or use recombinant erythropoietin growth factors but must not have active bleeding).
  - b. Liver: AST  $\leq 2 \times$  ULN (upper limit of normal), serum total bilirubin  $\leq 2 \times$  ULN (except for patients with Gilbert's Syndrome).
  - c. Renal: serum creatinine  $\leq 1.5$  mg/dL or estimated creatinine clearance  $\geq 60\text{ml/min}$  using Crockcroft-Gault estimation **using the formula**  
$$eC_{Cr} = \frac{(140 - \text{Age}) \times \text{Mass (in kilograms)} \times [0.85 \text{ if Female}]}{72 \times \text{Serum Creatinine (in mg/dL)}}$$

This

formula expects weight to be measured in kilograms and creatinine to be measured in mg/dL, as is standard in the USA.
  - d. Pulmonary: FEV1  $\geq 2.0$  liters or  $\geq 75\%$  of predicted for height and age. (PFTs are required for patients over 50 or with significant pulmonary or smoking history defined as  $>20$  pack years or history of COPD/emphysema).
  - e. Cardiac: No evidence of congestive heart failure, symptoms of coronary artery disease, myocardial infarction less than one year prior to entry, serious cardiac arrhythmias, or unstable angina. Patients who are over 40 or have had previous cardiac disease will be required to have a negative or low probability cardiac stress test for cardiac ischemia.
- 3.1.vii. Women should not be lactating and, if of childbearing age, have a negative pregnancy test within two weeks of entry to the study.

**3.1.viii.** Appropriate contraception in both genders (i.e., use of contraceptive strategies that prevent pregnancy; this most effectively would involve abstinence during the period of treatment but could include contraceptives, contragestives, and barrier methods.)

**3.1.ix.** The patient must be competent and have signed informed consent.

**3.1.x.** CNS: No history of cerebrovascular accident, transient ischemic attacks, central nervous system or brain metastases.

## **3.2 Exclusion Criteria**

**3.2.i.** Patients who have previously received IL-2 are not eligible. Patients on HCQ in neoadjuvant protocols or in the past for clinical indications ARE eligible, as are patients who have previously received CTLA-4 and/or PD-1/PD-L1 antibodies.

**3.2.ii.** Concomitant second malignancy except for non-melanoma skin cancer, and non-invasive cancer such as cervical CIS, superficial bladder cancer without local recurrence or breast CIS.

**3.2.iii.** In patients with a prior history of invasive malignancy, less than five years in complete remission.

**3.2.iv.** Positive serology for HIV, hepatitis B or hepatitis C

**3.2.v.** Significant co-morbid illness such as uncontrolled diabetes or active infection that would preclude treatment on this regimen.

**3.2.vi.** Use of corticosteroids or other immunosuppression (if patient had been taking steroids, at least 2 weeks must have passed since the last dose).

**3.2.vii.** History of inflammatory bowel disease or other serious autoimmune disease. (Not including thyroiditis and rheumatoid arthritis). Patients already on hydroxychloroquine for such disorders are not eligible.

**3.2.viii.** Patients with organ allografts.

**3.2.ix.** Uncontrolled hypertension (BP >150/100 mmHg).

**3.2.x.** Proteinuria dipstick > 3+ or  $\geq$  2gm/24 hours.

**3.2.xi.** Urine protein:creatinine ratio  $\geq$  1.0 at screening.

**3.2.xii.** Major surgery, open biopsy, significant traumatic injury within 28 days of starting treatment or anticipation of need for major surgical procedure during the course of the study.

- 3.2.xiii. Minor surgical procedures, fine needle aspirations or core biopsies within 7 days prior to starting treatment. Central venous catheter placements are permitted.
- 3.2.xiv. History of abdominal fistula, gastrointestinal perforation, or intraabdominal abscess within 6 months prior to starting treatment.
- 3.2.xv. Serious, non-healing wound, ulcer, or bone fracture.
- 3.2.xvi. History of tumor-related or other serious hemorrhage, bleeding diathesis, or underlying coagulopathy.
- 3.2.xvii. History of deep venous thrombosis, clinically significant peripheral vascular disease, or other thrombotic event.
- 3.2.xviii. Inability to comply with study and/or follow-up procedures.
- 3.2.xix. Individuals with known history of glucose 6 phosphate deficiency are excluded from the trial (possible issue with HCQ tolerance). No literature can be found to support hemolytic anemia having ever occurred in these patients and rheumatologists who frequently utilize this drug have not seen this as a side effect. Given that this has been a concern that has been raised, we believe it is prudent to exclude these patients with known G6PD deficiency from participation. These patients can receive IL-2 alone off trial.
- 3.2.xx. Patients with previously documented macular degeneration or diabetic retinopathy are excluded from the trial.
- 3.2.xxi. Baseline EKG with QTc > 470 msec (including subjects on medication). Subjects with ventricular pacemaker for whom QT interval is not measurable will be eligible on a case-by-case basis.

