### **2.2 High-dose IL-2 Therapy for Patients with RCC**

Investigations of IL-2 (Aldesleukin, Chiron) in patients with RCC were initiated by our group [Surgery Branch] at the NCI in the mid-1980s, and continued there and within the Cytokine Working Group. Initial studies evaluated high-dose bolus IL-2 therapy in combination with the infusion of autologous lymphocytes activated *ex vivo* in IL-2 (lymphokine-activated killer or LAK cells) (10, 11). While dramatic and durable responses were reported in some patients, subsequent studies found the efficacy of high-dose bolus IL-2 alone to be equivalent to that of the combination of IL-2 and LAK cells, prompting the abandonment of this more complex cellular therapy component.

In 1992, high-dose bolus IL-2 was approved by the FDA for the treatment of patients with metastatic renal cell cancer based on data presented on 255 patients entered onto 7 phase II clinical trials (8, 12). In these studies, 600,000-720,000 IU/kg of recombinant human IL-2 was administered by 15-minute infusion every 8 hours x 14 doses, thereby constituting a course of therapy. Patients received a course of therapy, consisting of two 5-day treatment cycles separated by 5-9 days of rest (maximum of 28 doses) (cycle 1A/1B). Courses were repeated every 8-12 weeks in stable or responding patients. Although 35% of patients received 720,000 IU/kg of IL-2 per dose and the remainder received 600,000 IU/kg per dose, the median cumulative amount of IL-2 administered was the same in both groups, since patients receiving 720,000 IU/kg per dose tolerated fewer IL-2 doses. Ninety-six percent of these patients had an ECOG performance status of 0 or 1, 85% had undergone a nephrectomy prior to starting IL-2 therapy, none had received prior immunotherapy, and the median time from diagnosis to treatment was 8.5 months.

Objective responses were seen in 37 of the 255 patients (RR 15%). There were 17 (7%) complete responses (CRs) and 20 (8%) partial responses (PRs). Fourteen of the responding patients (38%) began therapy with tumor burdens  $>50 \text{ cm}^2$  on pretreatment scans and 60% of PRs had  $>90\%$  regression of all measurable disease. The median duration of response was 54 months for all responders, 20 months for PRs and has not yet been reached for CRs. The median survival was 16 months for all 255 patients.

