## **2.4 Predictors of Clinical Benefit from Cytokine-Based Therapy**

Many groups have attempted to determine reliable predictors of response and survival for patients with metastatic renal cell carcinoma who were receiving immunotherapy. Factors that have been variably associated with response include performance status, number of organs with metastases (one versus two or more), absence of bone metastases, prior nephrectomy, degree of treatment-related thrombocytopenia, absence of prior interferon therapy, thyroid dysfunction, rebound lymphocytosis, erythropoietin production, and post-treatment elevations of blood TNF- $\alpha$  and IL-1 levels (17-20).

Motzer and colleagues have shown in patients receiving IFN that poor survival is associated with low Karnofsky performance status, high serum lactate dehydrogenase, low hemoglobin, high “corrected” serum calcium and time from initial renal cell carcinoma diagnosis to start of therapy of less than one year (20). In a cohort of 453 patients who received IFN as initial therapy, the median survival for the favorable (no risk factors), intermediate (one or two risk factors) and poor (three or more risk factors) risk groups were 30, 14 and 5 months respectively. Negrier and associates also identified independent predictors of rapid disease progression, defined as progression within 10 weeks of initiation of therapy (19, 21). These included greater than one metastatic site, disease-free interval of less than 1 year, and presence of liver metastases or mediastinal nodes, as well as type of immunotherapy used. Patients with liver metastases, more than one site of disease, and disease-free interval of less than 1 year had a lower response rate and a median survival of only 6 months, even while receiving combination IL-2 and interferon  $\alpha$  therapy. Figlin and colleagues identified prior nephrectomy and time from nephrectomy to relapse as important predictors of survival in patients receiving IL-2-based therapy (10). In their series, patients who received systemic immunotherapy for metastatic disease more than 6 months after nephrectomy had the best median survival and had a 3-year survival rate of 46%. A recent multivariate analysis by the same group of investigators that was confined to patients who received IL-2 after nephrectomy revealed survival to be inversely

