## 6.0 TREATMENT PLAN & SCHEMA

### 6.1 Classification:

Patients will be classified by the following criteria prior to entry and the historical cohort will be group-matched according to these criteria. (Each criterion is dichotomized as absent - 0 or present -1):

- lactate dehydrogenase > 1.5 upper limit of normal = 1
  - hemoglobin < lower limit of normal = 1
  - corrected calcium (>10mg/dL) (total calcium – 0.707\*[albumin-3.4]) = 1
  - Karnofsky performance status < 80% = 1
  - time from initial RCC diagnosis to start of protocol therapy < 1 year = 1
- | Patients        | # of Risk Factors | Median time to Death |
|------------------------|--------------------------|-----------------------------|
| Good Prognosis         | = no risk factors        | 30 months                   |
| Intermediate prognosis | = 1 or 2 risk factors    | 14 months                   |
| Poor prognosis         | = 3 or more              | 5 months                    |

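### Prior checkpoint-antibody treatment is allowed in the trial but absent from the matching and models of the historical comparison, so any difference in it is confounded with the HCQ effect

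*Combined protocol and SAP*

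**What the plan says.** **Who enters.** Section 3.2.i rules out one earlier immunotherapy: "Patients who have previously received IL-2 are not eligible". The same item accepts others, "as are patients who have previously received CTLA-4 and/or PD-1/PD-L1 antibodies". No limit, stratum or separate reporting is attached.

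**What is compared.** Objective 1.2 compares response, OS and PFS with published results for high-dose IL-2 alone and names Proclaim. Section 2.2 also offers the Select trial (123 patients, enrolled November 2006 to July 2009) as a comparison population with similar baseline characteristics. In 13.2.2, "Logistic and proportional hazards (Cox) regression will be used to compare clinical response, and OS and PFS, respectively", in order to examine what HCQ adds to IL-2.

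**What is balanced.** Under 6.1, "the historical cohort will be group-matched according to these criteria". The criteria are LDH, hemoglobin, corrected calcium, Karnofsky status and time from diagnosis. Section 13.2.2 lists no covariates, and 13.2.4 adds only this type of risk classification.

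**What is known about prior therapy in IL-2-alone patients.** For the 255-patient approval series, 2.2 says that "none had received prior immunotherapy". Median survival there was 16 months. Prior immunotherapy is not described for Proclaim, for Select, or for the 95 high-dose patients of the randomized trial in 2.3.

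**The concern.** The trial has one arm, so the effect of HCQ on OS, PFS and response can be read only against outside patients. That reading requires the two groups to be alike in whatever affects outcome on IL-2. Prior immunotherapy may be such a factor. Section 2.4 includes it in one form in its list of factors linked to response: "degree of treatment-related thrombocytopenia, absence of prior interferon therapy, thyroid dysfunction". If the trial contains checkpoint-treated patients and the comparator does not, or contains a different share, the fitted coefficient is the HCQ effect plus a case-mix difference. The plan as written can neither show nor remove that difference. A long washout would not cure it, because the issue is which patients are compared and not carry-over of the earlier drug.

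**Working it through.** **1. Do the planned adjustments cover prior therapy?** None of the five 6.1 factors is prior treatment. The nearest, time from diagnosis cut at one year, does not say what was given in the interval. Section 13.2.4 adds the risk classification and nothing else. The phrase on demographic and clinical covariates in 13.2.1 is unspecified and belongs to the within-trial cumulative logit model. Section 13 does not name prior therapy as covariate, subgroup or sensitivity analysis.

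**2. The plan's own survival figure.** Section 13.4 assumes that "the true median survival is 16 months", with 39 patients, 15 months of accrual and 15 more of observation. With exponential survival, λ = ln 2/16 = 0.0433 per month.
- P(event) = 1 − [exp(−15λ) − exp(−30λ)]/(15λ) = 0.616, so 39 × 0.616 = 24.0 events.
- Width of the 95% interval = 2 × 1.96 × 16/√24.0 = 12.8 months, the stated value.

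**3. How far case mix alone could move survival.** The pretreated share f and the relative death hazard h in pretreated patients are my assumptions; the documents give neither. I also assume an immunotherapy-naive comparator with a 16-month median and no HCQ effect.
- The mixed median solves (1−f)·exp(−λt) + f·exp(−hλt) = 0.5.
- Apparent hazard ratio = (expected events ÷ expected follow-up) ÷ λ.
- Example, f = 0.5 and h = 1.5: event probabilities 0.616 and 0.759, mean follow-up 14.22 and 11.68 months. (0.5×0.616 + 0.5×0.759)/(0.5×14.22 + 0.5×11.68)/0.0433 = 1.23.

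| f | h = 0.67: median, HR | h = 1.5: median, HR | h = 2.0: median, HR |
|---|---|---|---|
| 25% | 17.6 mo, 0.91 | 14.4 mo, 1.11 | 13.3 mo, 1.19 |
| 50% | 19.4 mo, 0.82 | 13.0 mo, 1.23 | 11.1 mo, 1.41 |
| 75% | 21.5 mo, 0.74 | 11.7 mo, 1.36 | 9.4 mo, 1.67 |

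**4. Complete response.** If pretreated patients have r times the naive CR rate and the comparator is naive, a true doubling appears as 2 × (1 − f + f·r). With f = 50%, r = 0.5 gives 1.5 and r = 1.5 gives 2.5.

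**5. Table 8.** Section 13.3.2 speaks of complete responses in one sentence, and of partial or complete responses in the criterion and the Table 8 caption. I computed the exact sequential binomial chance of halting at the looks at 18, 21 and 24 patients (bounds 0, 1, 1), with rate = base × (1 − f + f·r), on both readings:

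| Reading and base rate | none pretreated | 25%, half the rate | 50%, half | 50%, quarter |
|---|---|---|---|---|
| CR only, 16/95 (doubling of 8/95) | 11% | 17% | 24% | 34% |
| CR only, 16/95, starting from 1 CR in the first 5 (2.18) | 5% | 8% | 11% | 17% |
| PR or CR, 22/95 (no gain from HCQ) | 3% | 6% | 10% | 17% |

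These rows also assume that the base rate is that of naive patients, and show only the unfavorable direction.

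**The case against.** The strongest reply is that no mismatch is shown for the comparators actually named. Proclaim or Select may contain pretreated patients; the documents do not say, and 2.2 calls Select similar at baseline. That stands. It limits what can be claimed about the existence and size of a bias, but not the gap in the plan: whichever comparator is used, prior immunotherapy is neither matched nor modelled.

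The reply also notes that the primary objective is a single-arm CR proportion, valid for the mix enrolled, and that 13.2.2 describes the historical analyses as unpowered. That stands too and lowers the priority. Low power does not make a confounded estimate interpretable, however.

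A reader might infer three stronger points that the documents do not support:
- *The 16 months in 13.4 is a benchmark from naive patients.* The value equals the median of the 255-patient series, but 13.4 cites no source and uses it only to plan an interval width.
- *Pretreated patients will respond less.* The only support is prior interferon, in a list that 2.4 says is inconsistently linked to response. The end of 2.4 itself questions some of those studies. Interferon is not a checkpoint antibody, and the documents give no data on IL-2 after checkpoint therapy.
- *Table 8 would often halt a working regimen.* Section 2.3 does not say that the 8/95 patients were naive. The halting figures depend on which responses count and on whether the first five patients are included. They illustrate assumptions and carry no weight here.

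**Conclusion.** The point holds in a limited form. The trial admits checkpoint-treated patients without limit, the historical comparison has no prior-therapy term, and the one IL-2-alone series with a description of prior therapy had no prior immunotherapy. Any difference in prior immunotherapy is therefore inseparable from the HCQ effect in 13.2.2.

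Direction and size cannot be taken from the documents. Under the assumptions in the working (25% to 75% pretreated, relative hazard 0.67 to 2.0, naive comparator), case mix alone would yield apparent hazard ratios from 0.74 to 1.67. If the comparator had the same share of similar pretreated patients, this source of bias would vanish. Because the comparison is secondary and unpowered, this is a change to consider; it does not call the primary estimate into question.

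**What to change.** - **Baseline and 6.1:** record prior checkpoint antibody or other immunotherapy (yes/no) as a structured item and add it to the classification.
- **13.2.1:** next to the overall CR estimate, report CR with exact 95% confidence interval by this factor, labelled descriptive.
- **13.2.2:** state for each comparator whether prior immunotherapy is recorded. Where it is, match on it or include it as a covariate. Where the comparator is known to be immunotherapy-naive, add a sensitivity comparison restricted to naive trial patients. A published series without patient-level data allows only such restriction.

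The SAP should not describe the 8/95 prior as coming from naive patients, because the protocol does not say so.

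The cost is one history item and SAP wording, with no extra patients or procedures. The real price is precision. Section 2.18 implies 5 + 21 = 26 patients at 600 mg/d. If half were naive (an assumption), 2/13 = 15.4% has an exact 95% interval of about 2% to 45%, against 4% to 35% for 4/26. The naive-only result can therefore serve only as a sensitivity check.
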